In these experiments, visual stimuli (e.g., objects, scenes, simulated x-rays, magnified cell culture slide photographs, breast x-rays) are presented on a computer screen. On each trial, subjects examine the stimuli and indicate as quickly and accurately whether a target (e.g., a “tumor” or a “wrench”) is present or absent by pressing designated buttons. In some studies, observers will localize or describe targets rather than simply declaring them to be present or absent. In some experiments, there will be many different types of target (e.g. look for a chicken, a screw, a door, or a cup). In some experiments, there will be multiple instances of targets in the same display (e.g. find all the lung nodules in this chest x-ray). Search stimuli are usually continuously visible until observers choose to respond. In some experiments, stimuli are only briefly presented. Observers may be given feedback on their performance. This could include a point system designed to emphasize the importance of finding the target (e.g., negative points for false alarms and misses, as well as subtraction of 1 point/second, and positive points for hits). It could include a monetary payoff with money added for correct response and subtracted for errors. In no case would participant payment fall below \$8/hr. Subjects are typically given 50-100 practice trials and then tested in blocks of 200 - 1000 experimental trials with breaks in between and within blocks. Subjects are instructed before the task and debriefed after completion of the experiment. Some of our studies might also use a harmless (see below) eyetracker device, which measures eye movements. If eye movements are monitored when subjects are doing the task, an instrument will be recording the reflection of a beam of near-infrared light from their eye. This beam gives information about where their eyes are looking. Some of our studies may be conducted on-line. The experiment procedures will be very similar to those conducted in-person; however, eye movements will not be monitored in these studies. We will record observers' responses and reaction times. The experiments are hosted on-line, and subjects can access the experiment using a web link. Sometimes, an experimenter may assist or monitor the subjects during the study via an on-line

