To analyze the effect of one block on the next block, we derived all the pairs of blocks in the dataset. For each of the blocks, we calculated the true positive and false positive proportions and used these to derive the standard signal detection measure of d' and criterion (Note that we are refraining from using the term “sensitivity” because it is used to refer to d' in the behavioral science community and to the true positive rate in the medical community.) For the primary analyses, pairs were removed from analysis if either member of the pair produced a d' of less than 0.5. The task was relatively difficult and we had little control over the motivation of participants in online study of this sort. The probability of achieving a $d' > 0.5$ by guessing through an 80 trial block is $\sim 0.6\%$. A cutoff of 0.4 would permit over 2% of blocks to be pure guessing. A $d' > 0.5$ cutoff left 2,080 pairs of blocks. The distribution of those pairs is shown in

Table 5:

		Block N				
		Low, No Feedback	Low, Feedback	High, No Feedback	High, Feedback	
Block N+1	Low, No	29	140	151	134	454
	Low, Feed	92	110	150	218	570
	High, No	261	117	51	117	546
	High, Feed	147	218	118	27	510
		529	585	470	496	2080

Table 5: Counts of the 16 different pairs of Block N and Block N+1.

As can be seen, there is a good, if uneven distribution of pairs. There are fewer pairs on the diagonal where the condition is the same in Blocks N and N+1. In order to run the same block, twice in a row, participants needed to encounter that condition last on Day K and first on Day K+1 since the same condition could not be run twice on the same day. The marginals show that this distribution of the four different conditions is very roughly uniform.

First, we compare performance in the four conditions, regardless of their position the sequence of sessions for each observer. Figure 2 shows the signal detection measures of d' and criterion, “c”. These values cannot be computed if $p(\text{True Positive}) = 1.0$ or $p(\text{False Positive}) = 0.0$. Accordingly, in keeping with one standard practice, we add $\frac{1}{2}$ of a False Positive error to each False Positive count (Hautus, Macmillan, & Creelman, 2021).

[figure not shown]

Figure 2: D' and Criterion as a function of condition. Each dot represents one of 2080 blocks of data. Black lines show mean and +/- 95% CI of the mean.

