Even though participants were not focused on the speed of their responses, response time data reflect the effects of prevalence and feedback. Figure 3A shows the distribution of the ~300,000 trials, divided by block type. As is typical with RT distributions, these distributions have very long positive tails. Some very long RTs probably reflect extended thought, while others might reflect checking an incoming text message. We chose to eliminate the longest 1% of RTs as outliers (>7 sec). Figure 3B shows the mean and 95% confidence intervals on a much finer scale so that the differences between conditions are more clearly visible. There is a significant effect of block type ($F(3, 299422) = 52.88$, $p < 0.0001$, partial eta-sq = 0. 0.0005). Šídák's multiple comparisons test shows that the 46 msec difference between high and low prevalence with feedback is significant ($p < 0.0001$). Low prevalence RTs are shorter than high prevalence. Without feedback, the PICC effect on RT goes in the opposite direction. Low prevalence RTs are 18 msec longer than high prevalence ($p = 0.0008$). These effects are in line with the RT effects seen in other prevalence studies ([name] & VanWert, 2010).

[figure not shown]

Figure 3: Response time as a function of block type. RTs < 7 sec were analyzed. (A) RT distributions with the graph truncated at 3 sec. Black lines show the mean. (B) Mean RT on a much finer scale. Error bars show +95% confidence intervals.

How does one block influence the next?

The block data essentially replicate previous results, collected under very different conditions. However, the key question for this study is whether or not exposure to one combination of prevalence and feedback influences the next block of trials. Blocks could be independent of each other. The effect of one block might have a transient impact on the next block (e.g. lasting for a few trials and then fading). Finally, the effect of one block on the next could be dependent on the delay between blocks (especially since that delay could be from one day to the next.). To assess

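### The 18 ms no-feedback response-time difference called a PICC effect has no reported control for block order, and Table 5 shows that order is unbalanced for that pair of conditions

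*Combined protocol and SAP*

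**What the plan says.** In the Specific Protocol, under Statistical Analysis / Results, the condition comparison opens: "First, we compare performance in the four conditions, regardless of their position the sequence of sessions for each observer". Just before it, Table 5 counts adjacent pairs of blocks, with Block N in columns and Block N+1 in rows, and the text concludes: "The marginals show that this distribution of the four different conditions is very roughly uniform". The two rows that matter most are "Low, No 29 140 151 134 454" and "High, No 261 117 51 117 546".

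The RT results then report, for the conditions without feedback, "Low prevalence RTs are 18 msec longer than high prevalence" (p = 0.0008), and attribute this to PICC. The analysis is a one-way comparison of block type, F(3, 299422). The RT text mentions no term for block number, day or participant, and gives no first-block version.

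The corresponding criterion contrast (0.34 to 0.31) is reported as non-significant, p = 0.47. It was repeated on each participant's first block, where no PICC effect was found. The Methods section says contests were assigned at random, with no contest type repeated within a day, and names accuracy as the main dependent variable.

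**The concern.** Marginal totals tell the reader how often each condition occurs, not whether it tends to come before or after another. If responses get faster with experience, a condition that tends to be run before its comparator will look slower even when prevalence has no effect. The 18 ms difference has that direction: low prevalence without feedback is both the slower condition and the one that more often comes first in the direct pairs.

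Practice in early blocks is plausible here. Section V, Study Procedures, says of the programme in general: "Subjects are typically given 50-100 practice trials". The Specific Protocol describes no practice trials. The general text says only what is typical, so this is not a contradiction, but any early learning would fall inside the analysed trials.

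What is at stake is narrow. The introduction to the Specific Protocol says weak PICC effects are produced. The criterion evidence for that is null in all three reported forms: p = 0.47 with the d' filter, no effect in first blocks, and p = 0.1244 without the filter. The 18 ms RT difference is the only statistically significant between-condition result labelled PICC.

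**Working it through.** **Inputs.** The 16 cells of Table 5; the 18 ms contrast and F(3, 299422) from the RT results; 277,371 retained and 311,842 collected trials from the Observers section. LN and HN are low and high prevalence without feedback; LF and HF are the same with feedback.

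**1. Reproduce Table 5.** Row totals (Block N+1) are 454, 570, 546, 510. Column totals (Block N) are 529, 585, 470, 496. Both sum to 2,080, as printed.

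**2. Direct order within each prevalence contrast.**
- Without feedback: LN then HN 261, HN then LN 151, total 412. Chi-square = (261 − 151)² / 412 = 12,100 / 412 = 29.4; exact binomial p = 7e-8.
- With feedback: LF then HF 218, HF then LF 218. No imbalance.

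**3. Table as a whole.** Bowker's symmetry test gives 44.0 on 6 df, p = 7e-8. The Stuart-Maxwell test of the marginals is weaker: 8.8 on 3 df, p = 0.03. Block N minus Block N+1 is:
- LN: 529 − 454 = +75
- LF: 585 − 570 = +15
- HN: 470 − 546 = −76
- HF: 496 − 510 = −14

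These tests treat pairs as independent, although pairs overlap and participants repeat.

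**4. Check against random order.** In 1,000 simulations of random order with no repeat within a day, using Table 4 sequence lengths and thinning to 2,080 pairs, the LN/HN difference had SD 16.5 and never exceeded 53. The observed difference is 110. This check does not assume independent pairs. It does rely on Table 4, whose counts sum to 872 participants against the 630 stated, so it is approximate.

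**5. Where the imbalance sits.** Remove the LN/HN pairs and the nets reverse: LN 75 − 110 = −35; HN −76 + 110 = +34. LN also follows LF more often than it precedes it (140 against 92). The marginal imbalance therefore comes from one pair of cells.

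**6. Is Table 5 the RT dataset?** No. The RT analysis has 299,422 + 4 = 299,426 trials, or 299,426 / 311,842 = 96% of all trials. That is 22,055 more than the 277,371 retained after dropping participants without a full block. Table 5 holds only pairs in which both blocks passed the d' filter.

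**7. Break-even practice slope.** Slope needed = 18 ms / (LN-to-HN gap in mean block position). The documents do not give the gap, so it is varied:

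| Assumed gap (blocks) | Basis | Speeding needed per block |
|---|---|---|
| 0.076 | Table 5 marginals: 546/1,016 − 454/983 | 238 ms |
| 0.27 | the 412 direct pairs: 110/412 | 67 ms |
| 0.5 | assumption | 36 ms |
| 1 | assumption | 18 ms |

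These are the slopes that would produce the whole 18 ms. No practice effect is reported against which to judge them.

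**The case against.** The strongest reply is that Table 5 cannot carry much weight for RT. It gives adjacent order, not absolute position; it is filtered on d'; and it is not the RT dataset. On the marginals alone, 238 ms of speeding per block would be needed. The sentence on uniformity can fairly be read as a remark about frequency, and the text already calls the distribution of pairs uneven. RT is not the main dependent variable, and block type has a partial eta-squared of only 0.0005. All of this stands, and it limits the point to a possibility.

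Three stronger readings are tempting and are not supported:

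- *Low-prevalence no-feedback blocks come early and high-prevalence ones late.* The nets of +75 and −76 equal sequence starts minus sequence ends. They could reflect who starts with a condition, who stops after it, or both. The d' filter also splits sequences, so the start of a fragment need not be a person's first block. Mean positions and first-block shares are not identified.
- *The criterion contrast is confounded as well.* It is already reported as non-significant, and the first-block analysis, which removes position, found no PICC effect.
- *The d' advantage of high prevalence with feedback over high prevalence without is a practice artefact.* Direct order for that pair is balanced (118 against 117). If the no-feedback blocks did come later and practice helped, the bias would run against the reported difference.

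The document's own checks do not close the gap for RT. The first-block result is reported for criterion only. The restriction to each participant's first pair of blocks addresses unequal participation; it still mixes blocks 1 and 2, and no RT result from it is given.

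**Conclusion.** The point holds in a limited form. Conditions are pooled over position, near-uniform totals do not show balanced order, and the direct no-feedback prevalence pairs are clearly unbalanced (261 against 151) while the feedback pairs are not (218 against 218). The 18 ms difference is therefore open to a practice or order explanation that the reported analysis does not exclude.

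The size of any bias cannot be computed from the documents. It depends on the position gap in the RT dataset and on a practice slope, and neither is reported. That the bias would run in the reported direction assumes that responses speed up with practice and that the Table 5 imbalance carries over to the RT trials. The low prevalence effect with feedback and the main finding, that criterion carries over after a block with feedback, are not questioned on this ground. Severity is minor.

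**What to change.** - Tabulate condition by block number in the participant's own sequence, for the blocks that enter the RT analysis, and set this beside the statement about uniform marginals.
- Add block number and calendar day, with a participant effect, to the RT condition model; or report the no-feedback RT contrast on first blocks only, as was done for criterion.
- Describe the 18 ms as a PICC effect only if it remains.

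The study already analyses first blocks and the delay between blocks, so the order and timing data exist and the cost is a re-analysis. Standard errors may widen slightly, and the 18 ms may shrink. A first-block analysis would also use far fewer trials.

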Data were collected on-line via a free and open iOS application, “DiagnosUs”, created by Centaur Labs as a platform for game-like image labeling competitions <https://www.centaurlabs.com/>). Between 6/22/21 and 6/27/21, Centaur Labs ran 24 ‘contests’ on our behalf, collecting >300,000 trials from 803 participants in 6 days. Each of the 24 contests consisted of 80 unique images of a skin lesion as shown in Figure 1. This is a relatively small number of images, but it kept the sessions short and encouraged participation. Images came from the International Skin Imaging Collaboration (ISIC) 2018 challenge (Codella, et al., 2019). The set contains over 1,200 melanoma images and over 7,600 nevus images.

[figure not shown]

Figure 1: Sample stimulus displays. Left: Participants are asked if a lesion is a melanoma (cancer) or a nevus (benign ‘mole’). Right: After response, if this were a feedback condition, red or green feedback would inform the observer of the correctness of the answer. In no feedback conditions, neutral feedback indicated that the response had been registered.

On each of the six days, there were four contests available. These were:

- 1) Low Prevalence – No Feedback; consisting of 20% (16) melanoma images
- 2) Low Prevalence – Feedback; prevalence was the same as in #1, but with accurate, trial by trial feedback
- 3) High Prevalence – No Feedback; consisting of 50% (40) melanoma images
- 4) High Prevalence – Feedback; prevalence was the same as in #3, but with accurate, trial by trial feedback

The contests were randomly assigned to participants with the constraint that they did not run the same type of contest more than once in a day. Participants could take part in as many or as few contests as they wished over the course of the six days and they could end up repeating a

condition from one day on another day. The prevalence and feedback conditions were not advertised to participants. Accuracy is the main dependent variable though we also collected response times.

Because of the on-line, voluntary nature of the data collection, we did not have control over the viewing conditions or the type of screen used. We compensated by collecting a very large dataset (see below).

Observers

We collected data from 803 unique individuals. For each individual, we have a crude categorization of expertise as shown in Table 1:

Medical Student	337
Pre-Med Student	174
No Medical Experience	145
Medical Doctor	54
Other Healthcare Professional	47
Nurse	25

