A one-way ANOVA shows a main effect of condition on d' ($F(3, 2076) = 6.461, p = 0.0002$, partial eta-sq = 0.01) and Šídák's multiple comparisons test shows that performance on skin cancer detection task is modestly better in the high prevalence, feedback condition than in the high prevalence, no-feedback condition ($p = 0.008$). Prevalence effects are better understood as criterion shifts. An ANOVA shows a very large main effect of condition on criterion ($F(3, 2076) = 30.16, p < 0.0001$, partial eta-sq = 0.04). Pairwise comparisons show a strong LPE effect when feedback is given ($p < 0.0001$). Criterion becomes more conservative at low prevalence. Without

feedback, criterion becomes slightly more liberal on average (0.34 to 0.31). This is not statistically significant ($p = 0.47$). As noted earlier, the PICC effect (Levari, et al., 2018), while certainly real, is typically more fragile than the LPE effect in the opposite direction (Lyu, et al., 2021). The differences between conditions with feedback and without feedback are highly significant ($p < 0.0001$ for each comparison). A significant LPE effect is seen if analysis is restricted to each participant's first block of data ($p < 0.0001$). There is no PICC effect. If all blocks of data are used, eliminating the $d' > 0.5$ filter, there is, again a significant LPE ($p < 0.0001$) and an insignificant PICC effect ($p = 0.1244$).

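### The stated edge correction repairs a false-positive rate of 0 but not a true-positive rate of 1.0, so a perfect-hit block has no finite d' or criterion under the rule as written

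*Combined protocol and SAP*

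**What the plan says.** All references are to the specific protocol in the combined document.

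- **Statistical Analysis / Results.** True- and false-positive proportions are turned into d' and criterion for each block. "These values cannot be computed if" the true-positive proportion is 1.0 or the false-positive proportion is 0. The remedy given is that "we add $\frac{1}{2}$ of a False Positive error to each False Positive count". It is described as one standard practice, with a textbook citation. No change of denominator is mentioned, and nothing is said about the hit count.
- **Same section, d' filter.** A pair is removed if either block has d' below 0.5. There is no upper limit, so an infinite d' would pass.
- **Same section, Figure 2 and its tests.** "Each dot represents one of 2080 blocks of data", and "An ANOVA shows a very large main effect of condition on criterion ($F(3, 2076) = 30.16".
- **Methods.** Blocks have 80 images. Low-prevalence contests are described as "consisting of 20% (16) melanoma images", leaving 64 nevi. High-prevalence contests have 40 of each.
- **Does the effect of one block last throughout the next block?** The criterion analysis is repeated on each half of the second block.

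**The concern.** The text identifies two failures of the z-transform and repairs one. With a hit rate of 1.0, z is infinite, d' is infinite and criterion is minus infinity. Someone rescoring the posted data by the stated rule would have to invent a step at the first such block.

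The gap bears unevenly on the factor under study. A perfect hit rate is much easier to reach with 16 targets than with 40, and easier still with the roughly 8 targets in half of a low-prevalence block. If perfect-hit blocks are dropped, the most liberal blocks go, and more of them go at low prevalence. What is exposed is the reproducibility of the scoring and the size of the half-block criterion shifts (Figure 8). To a much smaller degree it also touches the low-versus-high contrast without feedback.

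**Working it through.** **1. Finite blocks.** 2,080 blocks in 4 conditions give error df 2,080 - 4 = 2,076, which matches both reported ANOVAs. Every analysed block therefore had a finite value. By second-block condition (Table 5 rows), 454 + 570 = 1,024 are low prevalence and 546 + 510 = 1,056 are high.

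**2. What the rule does.** Take d' = z(H) - z(F), c = -[z(H) + z(F)]/2 and F = (FP + 0.5)/nevi, with the denominator assumed unchanged. A count of FP = 0 becomes 0.5/64 (z = -2.42) or 0.5/40 (z = -2.24), so that case is repaired. H = 16/16 or 40/40 still gives z = infinity.

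**3. Choosing plausible values.** The text gives no mean or spread of d', but the d' filter gives a rough anchor.
- 2,988 blocks from 630 participants give 2,988 - 630 = 2,358 consecutive pairs. Keeping 2,080 removes 11.8%.
- Table 4 does not sum to 630. Taken at face value it gives 2,537 pairs, so 18.0% are removed.
- Simulated with d' SD 0.5, mean criterion 0.33 and independent blocks, the share of pairs removed is about 39% at mean d' 1.0, 22% at 1.25, 10-11% at 1.5 and 1.5% at 2.0.

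Mean d' of 1.25-1.5 brackets the observed 12-18%. Criterion SD is taken as 0.25-0.50.

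**4. Perfect-hit full blocks.** H = Φ(d'/2 - c).
- With no spread between blocks, d' 1.5 and c 0.33 give H = Φ(0.42) = 0.663 and H^16 = 0.14%, about 1.4 of 1,024.
- Spread raises this. The SD of d'/2 - c is √(0.25² + 0.25²) = 0.35 to √(0.25² + 0.50²) = 0.56.
- By simulation, before the d' filter, 0.7-3.7% of low-prevalence blocks are perfect-hit. On 1,024 blocks that is roughly 7 to 38. For high-prevalence blocks the figure is about 0.02% to under 0.7%, at most about 7 of 1,056.

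**5. Half-blocks.** Assume random target order (about 8 targets per low-prevalence half) and the d' filter applied to the full block. About 7-13% of low-prevalence halves are then undefined. If they are dropped, a true criterion shift of 0.10 is recovered as 0.074-0.093. With a log-linear correction it is recovered as 0.090-0.096.

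**6. The no-feedback contrast.** The text reports: "feedback, criterion becomes slightly more liberal on average (0.34 to 0.31", p = 0.47. The difference made by the stated rule (perfect-hit blocks dropped) compared with log-linear is about -0.003 to +0.006 at criterion SD 0.25-0.35, and up to +0.021 at SD 0.50.

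The reported p-value indicates which SD applies. With n = 454 and 546, p = 0.47 for a difference of 0.03 implies an observed SD of 0.29 if Šídák-adjusted over six comparisons. That is close to what a true SD of 0.25 produces (0.30-0.32). If unadjusted, it implies 0.65. The text does not say which.

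**The case against.** The strongest reply is that this is a reporting gap and that no fault in the results has been shown. All analysed blocks were finite, so perfect-hit blocks may not have occurred or may have been adjusted sensibly, and the attenuation figures apply only if they were dropped. The text itself says "The task was relatively difficult", and with no spread between blocks such cases would be rare. This stands as a limit on what can be claimed about the results. It does not rescue the rule, which as written fails in one of the two cases it was introduced to handle. With realistic spread, that case is likely to arise in full blocks and very likely in half-blocks.

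A reader might infer that the half-error biases criterion by prevalence, because at a false-positive rate of 0.10 it moves criterion by -0.034 with 40 nevi but only -0.022 with 64. The arithmetic is right at a fixed rate, but it is one component only. Small-sample bias in z(H) with 16 targets largely offsets it. At criterion SD 0.25-0.35 the net low-minus-high artefact is about -0.01 to +0.01, and log-linear is little different. It should not be presented as a net bias.

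A reader might also assume mean d' near 2.0, which gives larger effects. That setting predicts about 1.5% of pairs removed, far from the 12-18% implied by the document's own counts.

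**Conclusion.** The stated correction is incomplete and should be replaced, but no main conclusion is at risk. The low-prevalence effect with feedback (p < 0.0001) is far larger than any effect of the scoring rule. The block-to-block analysis subtracts a baseline from the same second-block condition, and the raw true- and false-positive proportions, which need no z-transform, show much the same pattern. Attenuation in half-blocks works against the persistence claim.

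It would be tempting to say that the scoring rule explains the missing concept-change effect without feedback. The documents do not support that. The contrast is non-significant with the filter (p = 0.47) and is an "insignificant PICC effect" without it (p = 0.1244), and the rule's contribution is probably near zero.

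What remains is a rule that cannot be followed as written and a modest understatement of half-block shifts at low prevalence if undefined halves were dropped. The sizes rest on assumed values: mean d' 1.25-1.5 with SD 0.5, mean criterion 0.33 with SD 0.25-0.50, independent blocks and random target order. The true number of perfect-hit blocks is not given.

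**What to change.** - Apply one symmetric correction to both rates in every block and half-block. Log-linear is an example: add 0.5 to the hit and false-positive counts and 1 to the target and non-target totals. State the denominators.
- Say how blocks with a true-positive rate of 1.0 were handled. Report the number with a true-positive rate of 1.0 and with a false-positive rate of 0, by condition, for full blocks and half-blocks. If there were none, say so.
- Re-run the d' filter, the Figure 2 contrasts with and without the filter, and the half-block tests.

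The cost is one change in the scoring code and a re-run on data already posted. d' shrinks slightly, and membership of the filtered set may change a little. Log-linear is one of several symmetric choices and is not bias-free: a small prevalence-dependent residual remains in the contrast, and a half-block shift of 0.10 is still under-recovered at 0.090-0.096.
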